### 10.4. Missing data

The impact of missing data in the main outcome will be analyzed by sensitivity analysis. Participants whose main variable has not been collected will be assumed to have a PC-AKI event for both arms, only for the oral group, and only for the intravenous group.

### 10.5. Deviations from the statistical plan

Any deviation from the statistical plan will be communicated to the IRB and the AEMPS and its approval will be requested by means of an amendment.

## **10.6. Selection of subjects for analysis**

All analyses will be by intention to treat and by protocol. Since the study is a non-inferiority study, the main analysis will be per protocol.

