### Experimental and control group

Experimental group: 500 mg capsules of sodium chloride (NaCl), supplied by the Pharmacy Department of the Hospital Universitario Ramón y Cajal. The total dose administered will be 100 mg/kg of body weight distributed in 60 hours, 48 hours before and 12 hours after the procedure. Appendix C describes the specific regimen according to weight.

Control group: 0.9% NaCl solution, supplied by the Pharmacy Department of the Hospital Universitario Ramón y Cajal. Dose: 3 ml/kg in the hour prior to the procedure and 2 ml/kg/hour in the following 4 hours.

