#### **4.2. Benefits and risks for humans**

The intended benefit is the demonstration that oral NaCl is non-inferior to an intravenous administration. This would allow the widespread application of a preventive treatment for contrast nephropathy, easy to administer to all patients. Likewise, the study could help us to identify patients at risk of PC-AKI analyzing the molecules mentioned.

The administration of saline compounds can increase blood volume and increase congestive symptoms such as edema. However, at the doses used and taking into account the criteria required for participation, patients are not expected to suffer any complication from the study. In any case, oral treatment, which is the subject of the study, should not produce more volume overload at the proposed doses than conventional intravenous treatment.

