### **5.3. Study design**

PNIC-Na is a phase 2, monocenter, randomized, open-label, non-inferiority trial. Two types of preventive treatment will be compared in patients undergoing a CE-CT scan:

- Oral prophylaxis with NaCl capsules and free water intake (250 mL of water with each capsule, ensuring a water intake of 750 mL/day) in the 48 hours prior to contrast exposure (n=133). It will be performed on an outpatient basis at a dose of 100 mg/kg body weight distributed in 60 hours, 48 hours prior to the procedure and 12 hours after. Appendix C describes the specific dose according to weight.
- Intravenous prophylaxis with 0.9% NaCl before and after contrast exposure (n=133). It will consist of in-hospital administration of 3 mL/kg in the hour before and 2 mL/kg in the 4 hours after the procedure.

The contrast used will be iodixanol (320 mg iodine/mL, infusion rate 2-5 mL/sec).

The corresponding treatment will be administered after medical prescription, validation by the pharmacist and confirmation. The nurse in charge of the patient will administer the treatment. The intravenous prophylaxis schedule for the study will begin in the Radiology Department of the Hospital, and will conclude in the Clinical Trials Unit of the same center.

The study will consist on the schedule of visits described in section 9.2.

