## 10. STATISTICAL CONSIDERATIONS

### 10.1. Sample size calculation

The sample size of the trial was calculated to be able to show the non-inferiority of oral sodium chloride to intravenous prophylaxis with regard to the primary study endpoint in outpatients undergoing a contrast-enhanced CT scan. The calculation was based on an expected PC-AKI incidence of 7% in the intravenous arm and 12% in the oral arm. Accordingly, considering a non-inferiority margin of 5%, a power of 80% and a one-sided p-value of 0.025, the required sample size is 266 patients, 133 per arm.

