### 10.3. Statistical methods

A description of the study sample stratified by randomly assigned treatment will be made. Categorical variables will be described by absolute and relative frequencies. Quantitative variables will be described by the mean and standard deviation (or median and interquartile range in the case of highly asymmetric distributions). For the analysis of the primary endpoint of the study, the univariate comparison of the proportions of PC-AKI events within 48 hours after intravenous contrast administration in both arms will be carried out. The 95% confidence interval of the difference in proportions will be calculated and displayed graphically. All analyses will be intention-to-treat and per-protocol. For the main objective a p-value less than 0.025 (unilateral) will be considered as statistically significant. All other group comparisons will be of an exploratory nature. Subgroup analyses will be performed for the risk factors defined as inclusion criteria. For exploratory contrasts, a p-value less than 0.05 (two-sided) will be considered as statistically significant.

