**APPENDIX C. SODIUM CHLORIDE ADMINISTRATION SCHEDULE ACCORDING TO WEIGHT**

With each oral dose, 250 mL of water should be administered, ensuring a minimum daily intake of 750 ml of water.

WEIGHT (Kg) and total dose	IV ADMINISTRATION (NaCl 0.9%)	ORAL ADMINISTRATION (NaCl capsules 500 mg)*	
50 - <55	550 mL	5 g (10 capsules)	
85 mEq	1 hour pre-test 150 mL 0-4 hours post-test 400 mL	48 hours pre-test 1 capsule 40 hours pre-test 1 capsule 32 hours pre-test 1 capsule 24 hours pre-test 1 capsule 16 hours pre-test 1 capsule 8 hours pre-test 2 capsules 0 hours 2 capsules 12 hours post-test 1 capsule	
55 - <60	605 mL	5.5 g (11 capsules)	
93,5 mEq	1 hour pre-test 165 mL 0-4 hours post-test 440 mL	48 hours pre-test 1 capsule 40 hours pre-test 1 capsule 32 hours pre-test 1 capsule 24 hours pre-test 1 capsule 16 hours pre-test 2 capsules 8 hours pre-test 2 capsules 0 hours 2 capsules 12 hours post-test 1 capsule	
60 - <65	660 mL	6 g (12 capsules)	
102 mEq	1 hour pre-test 180 mL 0-4 hours post-test 480 mL	48 hours pre-test 1 capsules 40 hours pre-test 1 capsules 32 hours pre-test 1 capsules 24 hours pre-test 2 capsules	

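### Per protocol is the main non-inferiority analysis; the planned ITT analysis has no stated role in the conclusion, and nothing says what follows if the two disagree

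*Combined protocol and SAP*

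**What the plan says.** Section 10.3 plans both analysis sets: "All analyses will be intention-to-treat and per-protocol". It gives one threshold for the main objective, one-sided p below 0.025, without naming a set. Section 10.6 repeats that both sets will be used and then ranks them: "Since the study is a non-inferiority study, the main analysis will be per protocol". The margin is 5 percentage points (sections 6.3 and 10.1).

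No section gives ITT a part in the non-inferiority conclusion or covers disagreement between the sets. The per-protocol exclusions are not listed. Capsule returns and IV quantities are recorded (5.8, 7.2), reasons for ending participation are listed (5.7, 6.4) and deviations are documented (14.2), but none of these is turned into an exclusion rule.

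Section 10.4 adds sensitivity analyses for missing outcomes: "Participants whose main variable has not been collected will be assumed to have a PC-AKI event for both arms, only for the oral group", and then for the intravenous group only.

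**The concern.** A per-protocol set is selected after randomisation. If selection is related to both arm and risk, the comparison is no longer the randomised one. Three features of this trial make that possible.

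- It is open-label, with different burdens by arm. Appendix C gives oral patients eight dosing times over 60 hours, from 48 hours before the scan to the last entries, for example "0 hours 2 capsules 12 hours post-test 1 capsule" in the lowest weight band. Most fall outside hospital. The IV arm is infused in hospital. Exclusions for non-adherence may therefore fall mainly on the oral arm, although late-found ineligibility, withdrawal or prohibited drugs can affect both.
- The sensitivity analyses in 10.4 concern patients with no outcome. A non-adherent patient whose creatinine was measured can leave the main analysis without any sensitivity analysis covering the exclusion.
- Section 4.2 describes the benefit sought as follows: "This would allow the widespread application of a preventive treatment for contrast nephropathy, easy to administer to all patients". The difference between arms as assigned bears on that aim, and ITT estimates it.

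At stake is a non-inferiority claim resting on a subset while the as-assigned comparison misses the margin, with no rule written in advance for that case.

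**Working it through.** **What the plan's figures supply.** Section 10.1: "The calculation was based on an expected PC-AKI incidence of 7% in the intravenous arm and 12% in the oral arm", margin 5 points, one-sided 0.025, 133 per arm. Those rates differ by exactly the margin (12 − 7 = 5), so they serve as the boundary case for the as-assigned difference. The figure of 133 cannot be reproduced in the plan's own direction, because the distance to the margin is 0.05 − 0.05 = 0. With a distance of 0.10 (sign reversed) the usual formula gives 133.98. That is a separate matter; here 133 is only the number randomised per arm.

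**Assumptions, not in the documents.** 13 or 27 patients excluded per affected arm (about 10% or 20% of 133), and the risk among them. The plan names no interval method, so Wald and Newcombe limits are both shown.

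**Method.** With arm risk p, excluded share f and excluded risk r, the retained risk is (p − f·r)/(1 − f). Exact binomial enumeration then gives the probability that the upper 95% limit for oral minus IV is below 5 points.

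Retained oral risk with r = 20%:
- 13 excluded: (0.12 − 0.0977 × 0.20)/(1 − 0.0977) = 11.1%
- 27 excluded: (0.12 − 0.2030 × 0.20)/(1 − 0.2030) = 10.0%

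Against 7% IV, the true retained difference is about 4.1 or 3.0 points, inside the margin, while the as-assigned difference stays at 5.

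**Chance of declaring non-inferiority, true as-assigned risks 7% IV and 12% oral.** ITT alone: 2.5% (Newcombe), 2.9% (Wald).

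| Exclusions (10% / 20%) | Per protocol alone, Newcombe | Per protocol alone, Wald | Both sets, Wald |
|---|---|---|---|
| Oral only, risk 20% | 3.9% / 6.6% | 5.2% / 10.3% | 2.6% / 2.6% |
| Both arms, risk 20% oral and 12% IV | 2.9% / 3.7% | 3.8% / 4.6% | 2.1% / 1.7% |
| Oral only, equal risk 12% | 2.3% / 2.1% | 3.1% / 3.5% | 2.3% / 2.1% |
| Oral only, lower risk 6% | below 2.5% | 2.1% / 1.4% | 1.9% / 1.3% |

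In the first two rows the excluded patients have about twice the risk of those retained (for example 0.20/0.111 = 1.8 and 0.20/0.100 = 2.0). Requiring both sets keeps the probability at about 2.6% or less throughout.

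**A disagreement in counts (Wald).** IV 10/133.
- Oral 9/133: difference −0.75 points, standard error 3.16, upper limit −0.75 + 1.96 × 3.16 = 5.44. ITT fails.
- Remove 13 oral patients with 2 events, leaving 7/120: difference −1.69, standard error 3.13, upper limit 4.45. Per protocol passes. The same flip occurs narrowly with Newcombe limits (5.79 to 4.96) and score limits (5.78 to 4.94).
- Reverse case: oral 8/133 gives 4.53 (ITT passes); removing 13 with no events leaves 8/120 and 5.47 (per protocol fails). This already fails under 10.6, so a both-sets rule changes nothing here.

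**Power cost, both true risks 7%, excluded patients at average risk (Wald).** Per protocol alone to both sets:
- Oral-only, 10%: 35.8% to 32.8%; 20%: 35.9% to 30.7%
- Both arms, 10%: 35.6% to 31.7%; 20%: 30.8% to 26.7%

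**The case against.** Section 10.6 makes an explicit choice and gives its reason: per protocol is main because the trial is a non-inferiority study. Both sets will be analysed, so a disagreement would be visible. Per protocol answers a legitimate question, whether the capsules work when taken as directed, and the sentence in 4.2 is a benefit statement that does not bind the trial to an ITT estimand. All of this stands, which is why the point is an improvement.

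The sizes are also soft. No document gives an exclusion share or a risk for excluded patients, and the largest figure depends partly on the Wald limit: 10.3% becomes 6.6% with Newcombe. The count example was chosen to flip. These objections limit the size. The direction in the higher-risk cases survives both interval methods.

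The means to judge adherence are not one-sided. The flowchart in 8.2 lists a compliance check at Visit 2 for all patients, and IV quantities are recorded. Only the criteria for exclusion are missing.

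Two stronger readings are tempting. A reader might infer that the plan states that per protocol alone decides and that an ITT failure is ignored. It does not: the threshold in 10.3 names no set, and the plan is silent on disagreement. Per protocol deciding is the default reading of the word main. A reader might also take 10.3% as the type I error of the planned test. It is not, because in that scenario the true difference among retained patients is inside the margin. The figure is measured against the as-assigned difference.

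**Conclusion.** The plan gives ITT no role in the conclusion and no rule for disagreement, so by default a per-protocol pass with an ITT failure could be reported as non-inferiority. A both-sets rule is a worthwhile improvement to a stated choice. The missing exclusion list is, taken alone, absent detail; it matters here because the main analysis rests on that set.

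The size depends on who is excluded. With 10% to 20% of oral patients excluded at a 20% risk, the chance of declaring non-inferiority at a true as-assigned difference of 5 points rises from 2.5–2.9% to between 3.9% and 10.3%. With similar exclusions in both arms it is 2.9% to 4.6%. At equal risk it is 2.1% to 3.5%, and at lower risk it is below 2.5%. The exclusion shares, the risks and the interval method are all assumptions. Confidence that the rule would matter in practice is moderate.

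**What to change.** In section 10.6, state that non-inferiority is declared only if the upper 95% limit for oral minus IV is below 5 points in both the ITT and the per-protocol sets. To make this workable, list the per-protocol exclusions for both arms and fix them before outcomes by arm are reviewed. Report the number excluded, and the events among them, by arm.

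The cost is mainly wording, since both analyses are already planned. The downside is about 3 to 5 points of power under the 7%/7% assumptions above, in a trial whose power there is already only about 31% to 36% per protocol, and a conservative rule when both arms lose patients.

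The sections do not agree on the post-procedure IV amount (compare the Summary and 4.5 with 5.3, 5.5 and 7.1). That is a separate point to be reconciled and is not part of this one.

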## **11. ACCESS TO SOURCE DATA AND DOCUMENTS**

All data collected for the study will be kept in the participating departments, in paper and electronic format. Clinical histories will be filed according to regulations or procedures established in the hospital. Data collected for the study will be identified by a code and only the principal researcher will be able to associate these data to the patient. Data will be included in a database that complies with Law 15/1999 on Personal Data Protection. Likewise, the transmission of data will be done with the appropriate security measures in compliance with that law and R.D. 1720/2007. Only the information from clinical history that is related to the study will be subject to verification. The research team is responsible for maintaining confidentiality. Only the sponsor, study physician/collaborators, health authorities (Spanish Agency of Medicines and Medical Devices), Clinical Research Ethics Committee and personnel authorized by the sponsor may check information always maintaining confidentiality in accordance to current legislation. Patients' identity will not be revealed if the results of the study are published.

## **12. QUALITY CONTROL AND ASSURANCE**

### **Monitoring visits**

At least 2 monitoring visits will be made during the study to ensure that all aspects of the protocol are followed. Source documents will be reviewed verify the information recorded in the EDC. Source documents are the original documents, data, and records. The investigator will ensure that the sponsor or the sponsor's representative have access to source documents. Documentation and aspects of the trial that can be reviewed: researcher's file, trial medication, medical records, informed consent, EDC and associated source documents. It is important that the researcher and study personnel are available during monitoring visits.

Independent on-site monitoring will be performed by the Unit of Clinical Research and Clinical Trials (UICEC) of Hospital Universitario Ramón y Cajal, ISCIII National Network (SCReN).

### **Health Authorities audits**

This study may be audited by the health authorities, AEMPS. If a health authority contacts the trial site for an inspection, the sponsor should be informed immediately. The researcher should guarantee the auditors access to all study documents for quality assurance.

## **13. ETHICAL ASPECTS**

### **13.1. General and specific rules for the investigators**

The investigators will strictly abide by the provisions of this protocol, filling out the data collection sheets, which will be sent in time to the sponsor or to the collaborating entity to analyze it. The trial will be carried out in accordance with the recommendations for clinical trials and evaluation of drugs in human, which appear in the Declaration of Helsinki (appendix A), revised in Tokyo, Venice, Hong Kong, South Africa, Edinburgh and Seoul (2008) and in the current Spanish legislation on clinical trials.

### **13.2. Informed consent**

All participating subjects will be informed and give their written consent before starting the study.. The volunteer will be given a copy of this informed consent sheet.

### **13.3. Security and confidentiality arrangements**

The information obtained by the implementation of the present study is considered confidential and should be treated as such at all times. The subjects of the study will be identified only with their subject code. In case of publication of the results of the study, the identity of the volunteers will not be revealed.

### **13.4. Content of the trial budget**

The financial compensation to the trial researchers is specified in the financial report, which is included as an appendix.

### **13.5. Insurance**

The Foundation for Biomedical Research of Hospital Universitario Ramón y Cajal has a civil liability insurance policy in accordance with Royal Decree 223/2004, which will provide compensation and indemnity to the participating subjects in case of damage to their health or injuries that may occur. In addition, this policy covers the responsibilities of the promoter, the research team and the Hospital Universitario Ramón y Cajal.

## **14. PRACTICAL CONSIDERATIONS**

### **14.1. Responsibilities of the participants of the clinical trial**

The investigators will follow the Good Clinical Practice guidelines and Service's standard operating procedures. All information collected during the trial should be recorded directly in the eDC. When a correction is made, date and initials of the person making the correction should be noted. Auxiliary personnel will follow the instructions given by the researcher regarding the extraction of blood samples and other complementary explorations. Patients should receive oral and written information regarding the design, purpose of the study and possible risks that may arise from it before enrolling in the trial. To participate in the study, they must sign their consent, although they can revoke it at any time and for any

reason. Patients will receive instructions to strictly respect the instructions. They will be informed of the need to contact if any incident arises during the study.

#### **14.2. Deviations from the protocol**

The researcher present in such circumstances will fully document the deviation and the reason in the EDC. When the deviation is related to inclusion/exclusion criteria, researchers will contact the clinical monitor by telephone to inform of the deviation.

#### **14.3. Storage of the study file**

All data will be kept on paper and in electronic form during 15 years after the end of the study.

This file should contain the following elements:

1. IRB/IEC approval of the protocol and informed consent form.
2. Copy of the written consent form and approved protocol with any amendments if applicable.
3. Any correspondence regarding the study with the sponsor, during the course of the study.
4. Any correspondence with the IRB/IEC.
5. List of IRB/IEC members who approved the study protocol.
6. Signed acceptance of the protocol.
7. Curriculum vitae of the research team.
8. Record of signatures of the members of the research team.
9. Serious AR communications.
10. Contract between the sponsor and the research team.
11. List of patients.
12. Copies of the EDC.

The documentation will be filed following the standard procedures of the Internal Medicine Department.

#### **14.4. Sample identification**

The study medication will be provided by the sponsor, and will be labeled according to recommendations of Royal Decree 223/2004.

#### **14.5. Amendments to the protocol**

Neither the investigator nor the monitor or the sponsor will modify this protocol without first obtaining the consent of the other parties. The modification should be documented in writing. Any changes in the research activity, except those necessary to eliminate an immediate apparent risk to the patient, should be reviewed and approved by the IRB/IEC prior to implementation. Amendments to the protocol should be submitted by the sponsor to the health authorities, and modifications may require review and approval by the IRB/IEC.

#### **14.6. Acceptance by the investigator**

The investigator commitment statement is included in section 2.

## **14.7. Conditions for publication**

The results derived from the present study will be published; the approval of the investigators and the sponsor will be required. The monitor and the sponsor should have a copy of the manuscript to be published 15 days before it is sent to the editor. Likewise, the confidentiality of the patient's identity will always be respected. The study sponsor undertakes to publish the results, whether positive or negative.

## **15. APPENDICES**

### **APPENDIX A. WMA DECLARATION OF HELSINKI**

#### **WORLD MEDICAL ASSOCIATION DECLARATION OF HELSINKI - Ethical Principles for Medical Research Involving Human Subjects**

Adopted by the 18th WMA General Assembly, Helsinki, Finland, June 1964, and amended by the: 29th WMA General Assembly, Tokyo, Japan, October 1975. 35th WMA General Assembly, Venice, Italy, October 1983. 41st WMA General Assembly, Hong Kong, September 1989. 48th WMA General Assembly, Somerset West, Republic of South Africa, October 1996. 52nd WMA General Assembly, Edinburgh, Scotland, October 2000. 53rd WMA General Assembly, Washington 2002 (Note of Clarification on paragraph 29 added). 55th WMA General Assembly, Tokyo 2004 (Note of Clarification on Paragraph 30 added). 59th WMA General Assembly, Seoul, October 2008.

#### **INTRODUCTION**

The World Medical Association (WMA) has developed the Declaration of Helsinki as a statement of ethical principles for medical research involving human subjects, including research on identifiable human material and data.

The Declaration is intended to be read as a whole and each of its constituent paragraphs should not be applied without consideration of all other relevant paragraphs.

Although the Declaration is addressed primarily to physicians, the WMA encourages other participants in medical research involving human subjects to adopt these principles.

It is the duty of the physician to promote and safeguard the health of patients, including those who are involved in medical research. The physician's knowledge and conscience are dedicated to the fulfilment of this duty.

The Declaration of Geneva of the WMA binds the physician with the words, "The health of my patient will be my first consideration," and the International Code of Medical Ethics declares that, "A physician shall act in the patient's best interest when providing medical care."

Medical progress is based on research that ultimately must include studies involving human subjects. Populations that are underrepresented in medical research should be provided appropriate access to participation in research.

In medical research involving human subjects, the well-being of the individual research subject must take precedence over all other interests.

The primary purpose of medical research involving human subjects is to understand the causes, development and effects of diseases and improve preventive, diagnostic and therapeutic interventions (methods, procedures and treatments). Even the best current interventions must be evaluated continually through research for their safety, effectiveness, efficiency, accessibility and quality.

In medical practice and in medical research, most interventions involve risks and burdens.

Medical research is subject to ethical standards that promote respect for all human subjects and protect their health and rights. Some research populations are particularly vulnerable and need special protection. These include those who cannot give or refuse consent for themselves and those who may be vulnerable to coercion or undue influence.

Physicians should consider the ethical, legal and regulatory norms and standards for research involving human subjects in their own countries as well as applicable international norms and standards. No national or international ethical, legal or regulatory requirement should reduce or eliminate any of the protections for research subjects set forth in this Declaration.

